9.3 VARIABLES

Variables analysed will include:

9.3.1 Collected/estimated through the HCP questionnaire

- Information related to HCPs/patients participation: contact rate, response rate, cooperation rate, and refusal rate (section 9.7)
- Variables related to HCPs practice information:
 - Duration of practice (year working with diabetic patients)
 - Specialty (GP, endocrinologist/diabetologist, pharmacist, internist, gastroenterologist, nurse, geriatrist)
 - Type of setting (office based, hospital based, both, outpatient pharmacy, hospital pharmacy, diabetes care clinic)

- Past experience with SULIQUA (number of patients treated with SULIQUA pre-filled pen)
- Variables related to the HCPs knowledge about the prescribing conditions and safety information/warnings of SULIQUA data include:
 - HCP knowledge about SULIQUA pre-filled pen guide for HCPs
 - Awareness of the responsibility to provide each patient with the guide for patient treated with SULIQUA
 - Knowledge of the instructions for appropriate utilization of SULIQUA pre-filled pen (dose titration, pen choice, storage, adverse reactions e)
 - Appropriate labelling of dose range and strength of SULIQUA pre-filled pen and dose steps to be administered in prescription (yes/no)
 - Education/Advice of the patient with regard to dose steps required, design features and appropriate utilization of SULIQUA pre-filled pen, close blood sugar levels monitoring after initiation, safety information
 - Number of recorded medication errors since EM distribution
- Receipt of SULIQUA pre-filled pen guide for HCPs (yes/no)
- Distribution to patients/caregivers of the guide for patient treated with SULIQUA (yes/no)

9.3.2 Variables collected through the patient questionnaire

Patient related variables include:

- Patients characteristics (age, gender, length of SULIQUA treatment)
- Treating physician (GP, endocrinologist/diabetologist, internist, gastroenterologist, geriatrist)
- Patient knowledge about SULIQUA pre-filled pen guide for patient (yes/no)
- Patient knowledge about SULIQUA pre-filled pen conditions of use (features and appropriate utilization of SULIQUA pre-filled pen, close blood sugar levels monitoring after initiation, safety information)

9.4 DATA SOURCES

The survey is a primary data collection conducted through two questionnaires administered by web, phone or paper:

- A HCP questionnaire (administered by web or phone)
- A patient questionnaire (administered by web or paper)

HCPs will be identified from OneKey lists (IQVIA).

The HCP questionnaire was developed and tested among 6 HCPs for its comprehensibility, consistency and the appropriateness of medical terms. HCPs' comments were implemented in the final version. Likewise, a patient/caregiver questionnaire was tested among 6 non-HCPs for optimal readability by patients.

The translated versions of the questionnaire from English into local languages was done using the back and forth method (from English into local language and then from local language back into English) to ensure an accurate translation.

The HCP and patient questionnaire completion is estimated to take about 15-20 minutes.

9.5 STUDY SIZE

9.5.1 Determination of sample size

The sample size formula based on the normal approximation to the binomial is the following:

$$n = \frac{P \cdot (1 - P) \cdot (Z_{1-\alpha/2})^2}{e^2},$$

Where P is the expected proportion, e is one half the desired width of the confidence interval (CI), and $Z_{1-\alpha/2}$ is the standard normal Z value corresponding to a cumulative probability of $1 - \alpha/2$. The following table provides the sample size for a margin error for 95% CI based on various half-widths and proportions of interest (Table 3).

Table 3: Sample size obtained for various precisions and various proportions

Proportion	Margin of error for 95% CI				
	8%	5%	4%	3%	2%
10%	55	139	216	384	864
30%	127	323	504	896	2017
50%	150	384	600	1067	2401
70%	127	323	504	896	2017
90%	55	139	216	384	864

The proportions of interest (p) are the proportions mentioned under specific objectives above. As p is not known in advance, we consider it to be 50% (maximum uncertainty). Such a hypothesis yields the most conservative i.e. the largest sample size for a specified margin of error.

HCPs to be enrolled:

According to the above sampling formula, the required sample size for the study would be 384 for a precision level of 5%. This sample will be divided into 3 waves, each comprising 128 HCPs and providing a precision of 8.66% for each wave based on the same formula. It is estimated that at least 85% of the questionnaires completed by HCPs will be analysable. Therefore, approximately 450 HCPs shall be surveyed in total. An overall sample of 150 HCPs will be needed for each wave.

Patients to be enrolled:

Applying the same rule, the required sample size would be 150 per wave for a precision level of 8%.

9.5.2 Sample distribution

Total sample of HCPs

A total sample of 450 HCPs is to be recruited for this study.

For the conduct of the survey, ideally the sample of 450 HCPs should be proportionally split between the selected countries based on the number of HCPs in each country. However, due to large variance of the number of HCPs in targeted countries such a distribution would yield to a number of participants in smaller countries and/or in specialties (such as endocrinologists) too small to allow the applicability of common statistical methods.

A pragmatic split will therefore be implemented in each wave to allocate a sufficient sub-sample size to the less represented countries based on the countries included in each wave of the survey.

To be representative, such a sample will necessitate that the results of the study be weighted back according to the real proportion of HCPs from IQVIA reference lists.

Total sample of patients

A total sample of 450 patients is to be recruited in the study.

With a similar line of reasoning as above, a pragmatic split will be implemented in each wave to allocate a sufficient sub-sample size to the less represented countries.

9.6 DATA MANAGEMENT

9.6.1 Data collection schedule

The data collection period will last for 6 months in each wave.

As the EM might not have been approved in each of the participating countries at the same time, the EM will be disseminated at different time periods in each country. Consequently, in the same wave the field work will be conducted at different time periods in each country. Whenever possible, the countries will be grouped, but effort will be made to conduct the survey between 6 and 12 months after the dissemination of the EM in each country.

The survey will be conducted by IQVIA Primary Intelligence, a division of IQVIA specialised in the conduct of phone and web surveys for more than 20 years. IQVIA Primary Intelligence will create a web-based instance survey. The lists of HCPs will be loaded into separate databases for the management of the survey. HCPs' answers/data will be collected through a web questionnaire. The survey will collect data in an anonymous manner.

HCPs will be randomly contacted, mainly by e-mails, and according to their stratum by the IQVIA Primary Intelligence team. Their recruitment will be done as follows:

- HCPs will be invited to participate in the survey (via e-mails, letters or phone calls). The survey background and objectives, the contact information for questions, and the proposed compensation will be explained to the HCPs at this step. The MAH will ensure that the compensation is in line with relevant guidelines of each country and that it only constitutes a compensation of the actual effort and time that is needed to fill-in the questionnaire.

- If they agree to participate in the survey, they will receive a link to access the survey and the instructions for the web questionnaire completion.
- HCPs can also choose to participate in the survey by phone. In this case, an appointment for a phone interview will be scheduled with them.
- If the questionnaire is not completed and sent to IQVIA Primary Intelligence, the HCPs will be sent a reminder by e-mail one week after the start of the survey.
- If the target is not achieved in the stratum, a reminder by phone will be conducted 1.5 week after the start of the survey.
- If the questionnaire has been started but is still not completed and sent to IQVIA Primary Intelligence, the HCPs will be sent a last reminder by e-mail 2 weeks after the start of the survey.

If necessary, i.e. if the minimum number of needed responders is still not reached, the recruitment will be continued by phone to achieve the target in a specific stratum.

An HCP will be considered as contacted if he/she has:

- Answered the web questionnaire and sent it back to IQVIA Primary Intelligence
- Refused to participate,
- Been tentatively reached at least 3 times and up to 5 times.

An HCP will be considered as unreachable if he/she has been contacted between 3 and 5 times without any answer.

For each HCP of the sample, the number of contacts, and the date and time when he/she completed the web questionnaire will be recorded. Recruitment in each stratum will be stopped when the target is reached. If the files have been exhausted in any particular stratum, recruitment in this stratum will be prematurely ended and a strategy will be determined to adjust the sample size with associated weighting.

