9.6.2 Approaches for increasing response rates

People are increasingly contacted to participate in web or phone surveys. The overall response rate of participation remains low according to international studies (2) (3) (4). Holbrook et al. showed that the response rate to surveys continues to decline over time, but a lower rate does not appear to reduce the representativeness of a demographic survey (4). Van Geest et al. conducted a systematic review of 66 published reports on efforts to perform for improving response rates (5). Two general strategies were explored: incentives-based approaches and survey design-based approaches. Financial incentives, even little ones, were effective in improving physician response rates while non-monetary incentives were much less effective. These measures include the use of a short questionnaire, and questionnaires personalised, and approved by professional associations.

In order to increase the response rate among HCPs, three actions will be applied to this survey:

- A compensation fee will be proposed to HCPs for their participation in the survey
- All HCPs will be sent an e-mail or contacted by experienced operators of IQVIA Primary Intelligence with extensive experience in conducting health related surveys
- Each HCP will be emailed or called up to 3-5 times before being considered as “not reachable”, and reminders will be sent by email if IQVIA Primary Intelligence does not receive the web questionnaire

For increasing the response rate among the patients:

- The survey will be explained clearly through the HCPs, and the documentation will also clearly explain the importance of the patients' participation
- It will be ensured that patients participate anonymously in the survey
- Patients will be given the option to take the survey by paper or web questionnaire
- Recruiting HCPs will be provided with 10 patient kits (as there is no limit on number of patients recruited by a HCP, a refill will be done at HCP's request)
- No monetary or material incentives will be provided to patients, but a compensation fee will be proposed to HCPs for each patient participating in the survey
- The response rate will be monitored throughout the data collection period. If at the end of the inclusion period, the number of participants is insufficient, the inclusion period will be extended. Reminder notices and additional kits will be sent to HCPs who have been invited to participate, but not yet recruited any patients.

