9.7.2 Secondary analysis

Analysis of Participation rate

The following cases of total response and non-response will be identified and described for HCPs:

- Targeted HCPs: HCPs reached to whom an e-mail or e-mail has been sent or have been called
- Contacted HCPs: HCPs who have received the e-mail or have answered the phone call.
- HCPs who agreed to participate: HCPs willing to participate in the survey (e.g. by phone or by clicking on the link provided in the recruitment e-mail) or in the patient's recruitment
- HCPs with submitted questionnaire: HCPs who actually answered the questionnaire through the end and submitted it. (One or some missing answers are allowed across the questionnaire.)
- HCPs who recruited patients: HCPs with at least 1 patient having actually answered the questionnaire and submitted it by paper or web

For patients/caregivers, more simplified definitions will be calculated based on the following definitions:

- Contacted patients/caregivers: those who have been asked by HCPs to participate
- Patients/caregivers who agreed to participate: those who accepted the questionnaire
- Patients/caregivers with submitted questionnaire: those who actually answered the questionnaire and submitted it by paper or web

The participation rates of HCPs will be examined via the following ratios:

- Contact rate = Number of contacted HCPs divided by the total number of targeted HCPs
- Response rate = Number of HCPs who agreed to participate (in the survey or in recruitment of patients) divided by the total number of invited HCPs
- Cooperation rate = Number of HCPs with submitted questionnaire divided by the total number of HCPs who agreed to participate
- Refusal rate = (Number of contacted HCPs minus the number of HCPs who agreed to participate) divided by the total number of contacted HCPs

The participation rates will be presented by country and specialty.

The screening log which includes the HCPs' characteristics will enable to compare the participating and non-participating HCPs' profile to check if there is a selection bias.

Effect of EMs variations among targeted countries on success factors:

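### Sections 9.6.1 and 9.7.2 define a contacted HCP differently, and under either definition the refusal rate counts silent HCPs as refusals

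*Protocol*

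**What the plan says.** Section 9.6.1 (data collection schedule) gives three alternative grounds for treating an HCP as contacted: a web questionnaire answered and returned, a refusal, or "Been tentatively reached at least 3 times and up to 5 times". It continues: "An HCP will be considered as unreachable if he/she has been contacted between 3 and 5 times without any answer". Section 9.6.2 uses the same number of attempts for the opposite status: "Each HCP will be emailed or called up to 3-5 times before being considered as" not reachable.

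Section 9.7.2 (secondary analysis) has its own list of groups, including "Contacted HCPs: HCPs who have received the e-mail or have answered the phone call". Two ratios use that group:

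- "Contact rate = Number of contacted HCPs divided by the total number of targeted HCPs"
- "Refusal rate = (Number of contacted HCPs minus the number of HCPs who agreed to participate) divided by the total number of contacted HCPs"

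The response rate in the same list is the number agreeing "divided by the total number of invited HCPs". For HCPs the list defines those targeted, contacted, agreeing, submitting a questionnaire and recruiting patients. It does not define those invited.

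**The concern.** A silent HCP with 3 to 5 attempts is both contacted and unreachable within 9.6.1. In 9.7.2 the same HCP is contacted or not, depending on whether an e-mail arrived. A phone-only non-answerer is contacted under the first section and not under the second.

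The refusal formula makes this matter. It does not count refusals. It takes everyone contacted who did not agree, so any silent HCP admitted to the contacted group becomes a refusal. Following 9.7.2 alone does not remove the problem: 9.6.1 says HCPs are contacted mainly by e-mail, and 9.9 accepts that an invitation may be filtered or sit in a mailbox that is rarely checked.

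Section 9.2.4.1 expects about ten HCPs to be approached for each analysable questionnaire, so most of those approached will not take part. The participation rates are meant to show why, by country and specialty. Two analysts working from the same contact log could report different contact and refusal rates, and neither refusal rate would separate people who declined from people who never replied.

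**Working it through.** The protocol states no contact or refusal rate, so there is no figure to reproduce. The check applies the 9.7.2 formulas under each definition.

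**Inputs**

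- Agreed: A = 150, taken equal to the HCP sample per wave in 9.5.1 (an assumption).
- Targeted: T = 10 × 150 = 1,500, from the approximate ten-to-one ratio in 9.2.4.1.
- Silent: 60% of those targeted, or 900. The protocol gives no such figure, so this is an assumption and is varied below.
- HCPs who answered: 1,500 − 900 = 600, of whom 150 agreed and 450 declined.

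**Formulas**

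- Contact rate = C / T
- Refusal rate = (C − A) / C, where C is the number contacted

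**Section 9.7.2.** Let f be the share of the 900 silent HCPs who received the e-mail. Then C = 600 + 900f.

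| f | C | Contact rate | Refusal rate |
|---|---|---|---|
| 0 | 600 | 40% | 450/600 = 75.0% |
| 0.5 | 1,050 | 70% | 900/1,050 = 85.7% |
| 0.9 | 1,410 | 94% | 1,260/1,410 = 89.4% |
| 1 | 1,500 | 100% | 1,350/1,500 = 90.0% |

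The number who actually declined is 450 in every row. Only e-mail delivery changes.

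**Section 9.6.1.** Silent HCPs enter C once they have had 3 to 5 attempts. If all 900 have, C = 1,500, the contact rate is 100% and the refusal rate is 1,350/1,500 = 90%. If some have had fewer than 3 attempts, C is smaller and both rates fall. These two figures are therefore upper bounds.

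**Varying the silent share.** With silent HCPs left out of C altogether:

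| Silent share | Contact rate | Refusal rate |
|---|---|---|
| 0% | 100% | 90.0% |
| 20% | 80% | 87.5% |
| 40% | 60% | 83.3% |
| 60% | 40% | 75.0% |
| 80% | 20% | 50.0% |
| 85% | 15% | 33.3% |

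The 9.6.1 ceiling stays at 90% refusal and 100% contact in every row, so the possible distortion grows with the silent share.

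**Response rate.** In the 60% case, reading invited as targeted gives 150/1,500 = 10%. Reading it as those who answered gives 150/600 = 25%.

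**The case against.** The strongest reply is that 9.7.2 defines contacted for itself, directly above the ratios, so the fieldwork rule in 9.6.1 need not enter the analysis. This stands in part. A reader might infer that every unreachable HCP will be reported as a refusal. The documents do not fix that: it follows only if the 9.6.1 rule is carried into 9.7.2 and every silent HCP has had at least 3 attempts. Under 9.7.2, unanswered calls and undelivered e-mails stay out. Delivered but unanswered e-mails still count as refusals, so the defect is reduced but not removed.

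A reader might also infer that the selection-bias assessment fails. It does not. The abstract, 9.7.2 and 9.9 base that assessment on comparing the characteristics of participants and non-participants, which does not use the contacted group. No section assigns the refusal rate to it.

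Three objections to the size are fair:

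- The schedule in 9.6.1 does not guarantee three attempts. The phone reminder depends on the stratum missing its target, the last e-mail goes only to those who have started the questionnaire, and recruitment stops once the target is met.
- Section 9.7.2 counts as agreeing anyone who clicks the link or is willing to recruit patients. The number agreeing can therefore exceed 150, which lowers the refusal rate.
- The ten-to-one ratio refers to analysable questionnaires, 128 per wave in 9.5.1, which gives 1,280 approached. The percentages do not change, since (1,280 − 128)/1,280 is also 90%.

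HCPs screened out after clicking the link already count as agreeing. They lower the cooperation rate and do not raise the refusal rate.

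Finally, 9.6.1 names refusal as an outcome of its own and 9.8.5 says contacts are traced. The information is not lost; the formula does not use it.

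**Conclusion.** The inconsistency is real and stands in the current text. Both definitions let silence count as refusal, for different sets of HCPs. With 1,500 approached, 150 agreeing and 60% silent (all assumed), the refusal rate under 9.7.2 lies between 75% and 90% and the contact rate between 40% and 100%, with e-mail delivery as the only driver. Under 9.6.1 they are at most 90% and at most 100%.

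The damage is confined to secondary descriptive rates. The success factors, the 80% rule, the sample size and the comparison of participants with non-participants do not depend on the definition. The undefined denominator of the response rate is a smaller slip of the same kind. Severity is minor.

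**What to change.** - In 9.6.1, remove the no-reply ground from the definition of contacted.
- Use one definition in 9.6.1 and 9.7.2: an answer from the HCP by any channel.
- Report HCPs who never answered as a separate non-contact category.
- In 9.7.2, set the refusal rate to explicit refusals divided by contacted HCPs.
- In the response rate, replace invited by targeted, which is already defined.

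In the illustration this gives a contact rate of 600/1,500 = 40%, a refusal rate of 450/600 = 75% and a response rate of 150/1,500 = 10%, whatever share of the e-mails was delivered.

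The cost is a wording change in two sections. Section 9.6.1 already records the number of contacts per HCP and recognises refusal as an outcome, 9.8.5 traces e-mails and calls, and 9.7.2 relies on a screening log. No further data collection should be needed.

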9.6.2 Approaches for increasing response rates

People are increasingly contacted to participate in web or phone surveys. The overall response rate of participation remains low according to international studies (2) (3) (4). Holbrook et al. showed that the response rate to surveys continues to decline over time, but a lower rate does not appear to reduce the representativeness of a demographic survey (4). Van Geest et al. conducted a systematic review of 66 published reports on efforts to perform for improving response rates (5). Two general strategies were explored: incentives-based approaches and survey design-based approaches. Financial incentives, even little ones, were effective in improving physician response rates while non-monetary incentives were much less effective. These measures include the use of a short questionnaire, and questionnaires personalised, and approved by professional associations.

In order to increase the response rate among HCPs, three actions will be applied to this survey:

- A compensation fee will be proposed to HCPs for their participation in the survey
- All HCPs will be sent an e-mail or contacted by experienced operators of IQVIA Primary Intelligence with extensive experience in conducting health related surveys
- Each HCP will be emailed or called up to 3-5 times before being considered as “not reachable”, and reminders will be sent by email if IQVIA Primary Intelligence does not receive the web questionnaire

For increasing the response rate among the patients:

- The survey will be explained clearly through the HCPs, and the documentation will also clearly explain the importance of the patients' participation
- It will be ensured that patients participate anonymously in the survey
- Patients will be given the option to take the survey by paper or web questionnaire
- Recruiting HCPs will be provided with 10 patient kits (as there is no limit on number of patients recruited by a HCP, a refill will be done at HCP's request)
- No monetary or material incentives will be provided to patients, but a compensation fee will be proposed to HCPs for each patient participating in the survey
- The response rate will be monitored throughout the data collection period. If at the end of the inclusion period, the number of participants is insufficient, the inclusion period will be extended. Reminder notices and additional kits will be sent to HCPs who have been invited to participate, but not yet recruited any patients.

